### LIST OF ABBREVIATIONS AND DEFINITION OF TERMS

Term or Abbreviation	Description
6 $\beta$ N	6- $\beta$ -naltrexol
ADR	Adverse Drug Reaction
AE	Adverse Event
AUC	Area Under the Curve
CRF	Case Report Form
CRO	Contract Research Organization
CSSRS	Columbia Suicide Severity Rating Scale
DSMB	Data Safety Monitoring Board
eCRF	Electronic Case Report Forms
EUC	Electrolytes, Urea, Creatinine
FBE	Full Blood Examination
FDA	Food and Drug Administration
GCP	Good Clinical Practice
GHQ	General Health Questionnaire
GLP	Good Laboratory Practices
GMP	Good Manufacturing Practices
HCV	Hepatitis C Virus
HIV	Human Immunodeficiency Virus
HREC	Human Research Ethics Committee
IB	Investigator's Brochure
ICH	International Council for Harmonization
IP	Investigational Product
IRB	Institutional Review Board
LFT	Liver Function Tests
MHA	Mental Health Assessment
NCT	Naloxone Challenge Test
NTX	Naltrexone
NYSPI	New York State Psychiatric Institute
OLANI	O'Neil Long Acting Naltrexone Implant
PI	Principal Investigator
PIC	Participant Information Consent
PK	Pharmacokinetic
QC	Quality Control

**A PHARMACOKINETIC STUDY OF VIVITROL IN HEALTHY PARTICIPANTS**

CONFIDENTIAL

Go-Medical Protocol GM 0019: Ver.0.5\_25 MAR 2021

Term or Abbreviation	Description
SAE	Serious Adverse Event
SOP	Standard Operating Procedure
UDS	Urine Drug Screen

## V. PROTOCOL SUMMARY

Title:	A PHARMACOKINETIC STUDY OF VIVITROL IN HEALTHY PARTICIPANTS
Overview:	
This is a Phase I, single-center, single arm, open-label study, to establish the pharmacokinetic (PK) parameters of Vivitrol 380 mg IM injection (IP), a US Food and Drug Administration (FDA) approved medication. Participants will be healthy volunteers with no significant medical or mental health disorders, who have completed participation in clinical trial GM 0017 (i.e. have received the OLANI treatment and have subsequently provided two consecutive plasma levels of naltrexone (NTX) <0.1ng/mL).
 
This study will examine the PK profile of Vivitrol IM 380 mg over 6 doses for a treatment period of 196 days. Intense sampling will occur after the 1st and 6th dose of Vivitrol. Participants will be without a DSM 5 - Substance Related Disorders classification. Participants will be required to undergo a Naloxone Challenge Test (NCT) to confirm opiate naïvety before administration of the IP. No randomization will occur.
 
Note: In the future, an expansion of this protocol is planned in order to include additional participants that initially receive 2 doses of Vivitrol followed by the OLANI treatment (i.e. the ‘cross-over’ group). This expansion may occur under this same protocol ID or a new protocol ID.

Objectives:	
Primary:
 
 
To determine the PK parameters of <math>C_{max}</math>, <math>T_{max}</math>, <math>C_{trough}</math> (Day 28), and AUC for the 1st and 6th dose of Vivitrol IM 380mg.
 
 
Secondary:
 
 
To determine steady state characteristics and demonstrate no accumulation between repeat doses.
 
To establish the safety and tolerability of the NTX injection over 6 months.
 

Endpoint:	
Primary:
 
 
PK parameters, including <math>C_{max}</math>, <math>C_{trough}</math> (Day 28), and AUC
 
 
Secondary:
 
 
To demonstrate no accumulation following repeat doses of Vivitrol IM 380 mg.
 
 
Safety endpoints will be captured through 6 months and will include the incidence of adverse events (AEs) including:
 
 
deaths
 
serious adverse events (SAEs)
 
AEs leading to discontinuation
 
common AEs
 

**A PHARMACOKINETIC STUDY OF VIVITROL IN HEALTHY PARTICIPANTS**

CONFIDENTIAL

Go-Medical Protocol GM 0019: Ver.0.5\_25 MAR 2021

	

• AEs of special interest (injection site reactions and hepatic effects)

• laboratory abnormalities (absolute values and changes over time in laboratory parameters)

• the proportion of participants who discontinue treatment due to AEs)

Population:	Up to 6 healthy participants to be recruited (with 4 required to complete the study), aged at least 18 ( $\geq 18$ ) and no older than 57 ( $< 58$ ), without a DSM 5 - Substance Related Disorders classification, residing within the New York metropolitan area. Participants are to be recruited with the perquisite of having successfully finished study GM 0017.
Phase:	I
Number of Sites:	Two Site 1: New York State Psychiatric Institute, [name] (administration center for PI) Site 2: Clinilabs, [name] (Vivitrol reference dose administration and follow-up visits)
Investigational Product:	The investigational product (IP) (intended reference product) is a Vivitrol Intramuscular injection, 380 mg (six doses given 28 days apart)
Study Duration:	Estimated 9 months
Participant Duration:	196 days

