## 4 STUDY DESIGN AND ENDPOINTS

### 4.1 DESCRIPTION OF THE STUDY DESIGN

Participants who have completed the study end points of GM 0017 (i.e. two consecutive monthly plasma results <0.1 ng/mL for NTX) will be offered enrolment into the study.

Up to 15 participants will be recruited onto this arm with 12 expected to complete to full dosing and sampling schedule.

Participants will receive a 380 mg Vivitrol IM injection and blood samples will be taken according to the sampling schedule of Table 7-1. Subsequently, participants will be re-administered Vivitrol injections every 28 days for a total of 6 Vivitrol injections. Blood sampling will be performed as per Table 7-1. The administration of 6 repeated Vivitrol injections is to confirm the published findings that no accumulation of Vivitrol is evident after repeated injections and to allow a direct time frame comparison to future bioequivalence study with OLANI.

This PK information, including day 28 naltrexone trough level, is needed so that Vivitrol can be used as the reference product for previous and future studies of OLANI.

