### 5.3 STRATEGIES FOR RECRUITMENT AND RETENTION

#### 5.3.1 *Target Sample Size*

Recruitment into the study will be solely offered to the 19 participants who have completed the previous study GM 0017. Up to 15 participants from GM 0017 will be targeted for recruitment to this study. We expect that 12 of the 15 participants will complete the study (80%), which is providing at least 75% valid PK blood samples including Day 28 and Day 168 Vivitrol trough levels.

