#### ***7.3.7 Unscheduled/Late Visits***

It is anticipated that some participants may miss or be delayed to some of their appointments. Every effort will be made to obtain blood samples at the scheduled dates, but blood samples will be accepted if they are taken late, with allowances made in the statistical analysis. Participants who miss appointments will be contacted by phone to encourage them to return

for as many appointments as possible. However, some dropouts are also anticipated so additional participants have been recruited to aim for a total of 4 completers.

Participants will be asked to complete the following as a minimum; concomitant medication review, Vital signs, PK blood collection and AE monitoring.

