### **10.5 SAMPLE SIZE**

At the completion of the study, it is desirable that a minimum of 12 participants will complete a minimum of 75% blood collection time points.

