**17 REVISION HISTORY**

Date	Version Number	Reason for Revision
N/A	0.1	N/A. New document that was submitted in a Meeting Package to the FDA. This version was never implemented.
01 October 2020	0.2	Reduced the scope of the protocol to focus only on Vivitrol assessments in a small number of participants completing study GM 0017.
27 October 2020	0.3	Updated to incorporate changes requested by the FDA.
17 December 2020	0.4	Updated to incorporate changes requested by the reviewing IRB and those made by the study team during development of the database.
25 March 2021	0.5	The primary reason for this amendment is to expand the number of participants. Enrollment of at least 15 participants will provide more PK data and funding is now available to support this larger N.

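### The version 0.5 enrolment increase did not reach the Protocol Summary or Section 7.3.7, which still give 6 recruits and 4 completers against 15 and 12 elsewhere

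*Combined protocol and SAP*

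**What the plan says.** Two places carry the smaller figures.

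- Protocol Summary (Section V), Population row: "Up to 6 healthy participants to be recruited (with 4 required to complete the study". The page is headed version 0.5, 25 March 2021.
- Section 7.3.7 (Unscheduled/Late Visits), on anticipated dropouts: "additional participants have been recruited to aim for a total of 4 completers". This section gives no recruitment number.

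Three places carry the larger figures.

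- Section 4.1: "Up to 15 participants will be recruited onto this arm with 12 expected to complete to full dosing and sampling schedule".
- Section 5.3.1: "Up to 15 participants from GM 0017 will be targeted for recruitment to this study", with 12 of the 15, stated as 80%, expected to complete. The same section gives the source of participants: "Recruitment into the study will be solely offered to the 19 participants who have completed the previous study GM 0017".
- Section 10.5: "it is desirable that a minimum of 12 participants will complete a minimum of 75% blood collection time points".

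The revision history (Section 17) says of version 0.5: "The primary reason for this amendment is to expand the number of participants". The Section 18.4 table names Sections 4.1, 5.3.1 and 10.5 as the places changed for the increase. It does not name the Protocol Summary or Section 7.3.7 for that change.

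**The concern.** The recruitment cap and the completer target are the only sample-size figures in this protocol, and each has two values depending on where one reads.

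The cap is an operative limit. Section 14.3 treats any noncompliance with the protocol as a deviation. Enrolling a seventh participant would therefore comply with Section 4.1 and breach the Summary. In the same way, a study that ended with 4 completers would meet the Summary and Section 7.3.7, yet fall well short of Section 10.5. A site, an IRB or a monitor working from the Summary would hold a different study size from the one the amendment was written to introduce.

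**Working it through.** **Inputs**

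| Place | Recruitment cap | Completers |
|---|---|---|
| Protocol Summary, Population | 6 | 4 (required) |
| Section 7.3.7 | not given | 4 (aim) |
| Section 4.1 | 15 | 12 (expected) |
| Section 5.3.1 | 15 | 12 (expected, 80%) |
| Section 10.5 | not given | at least 12 (desirable) |

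**Step 1: reproduce the plan's own figure.** Completion rate = 12 / 15 = 0.80, as Section 5.3.1 states. In reverse, 12 / (1 − 0.20) = 15. Sections 4.1, 5.3.1 and 10.5 therefore agree with one another.

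**Step 2: compare the two sets.** Recruitment: 15 − 6 = 9. Completers: 12 − 4 = 8. The Summary's pair implies 4 / 6 = 66.7% completion, not 80%, so it is not the same plan stated in other terms.

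**Step 3: can both sets hold?** With a cap of 6, completers cannot exceed 6, and 6 / 12 = 50% of the figure in Section 10.5. The target of 12 is twice the Summary's cap. A target of 4 is 4 / 12, or one third, of the Section 10.5 figure.

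**Step 4: does anything in the documents reconcile them?**

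- The Summary does not describe a subset. The study is single arm, and the Population row describes the whole of it.
- The future cross-over expansion mentioned in the Summary and Section 2.2 concerns other participants, who would receive Vivitrol before OLANI. Section 5.3.1 draws all 15 from GM 0017.
- The number of people to whom enrolment is offered does not force a cap of 6. Section 5.3.1 gives 19, and 15 is below 19.
- The row was edited for version 0.5. The age wording that Section 18.4 lists for this version stands in the same Population cell as the 6 and the 4.

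**Step 5: power and precision.** Section 10.2 (hypotheses) is marked not applicable, and no alpha, power, effect size, standard deviation or margin is given. No loss of power can be computed, and none is claimed.

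**The case against.** The strongest reply is that this is stale text with an undisputed answer. The sections that govern design and size agree, the revision history confirms the intent, Section 7.3.7 mentions completers only in passing, and no analysis depends on the number. All of that is true. It makes the correction easy, but it does not remove the conflict: the Summary is where readers look for the enrolment cap, and its cap rules out the target in Section 10.5.

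Four narrower points stand and limit how the finding should be put.

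- Section 10.5 calls 12 completers desirable. It is a target, and missing it breaks no stated rule.
- The 19 are people who completed GM 0017 and are offered enrolment. They must still meet Sections 5.1 and 5.2 and pass the naloxone challenge, so the number actually eligible is not stated.
- The places do not define a completer identically. Section 4.1 refers to the full dosing and sampling schedule. Section 5.3.1 asks for at least 75% valid PK samples including the Day 28 and Day 168 troughs. Section 10.5 asks for 75% of time points without naming the troughs. The Summary's Population row and Section 7.3.7 give no definition. These differences do not explain 4 against 12, because under any definition a cap of 6 excludes 12 completers.
- The Summary says 4 are required, whereas Sections 4.1 and 5.3.1 say 12 are expected. Copying the later wording changes the status of the figure as well as its value.

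**Conclusion.** The concern holds. Two current places in version 0.5 contradict three others: 6 against 15 for the recruitment cap and 4 against 12 for completers. The Summary's cap makes the Section 10.5 target unattainable, since at most half of it could be reached.

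The conclusion needs no outside figure. That 15 and 12 are the intended values rests on the agreement of Sections 4.1, 5.3.1 and 10.5; the revision history is used only to confirm the intent.

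This must be fixed, because the cap and the target are figures the trial is run by. The consequence is confined to conduct and reporting: how many people may be enrolled, and when the study counts as complete. If Sections 4.1, 5.3.1 and 10.5 are followed, no analysis changes.

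**What to change.** Make two wording corrections.

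1. Protocol Summary, Population row: replace the recruitment cap of 6 with 15, and the 4 required to complete with 12 expected to complete. This matches Sections 4.1 and 5.3.1. The sponsor should confirm the move from required to expected as a deliberate choice.
2. Section 7.3.7: replace the aim of 4 completers with 12.

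Leave Section 10.5 as it is. The cost is a text correction in two places. It needs no participants beyond those already planned in Sections 4.1 and 5.3.1, and no change to procedures or analysis.

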**VI. SCHEMATIC OF STUDY DESIGN**

Screening and recruitment	Naloxone challenge test	IP administration Vivitrol 380 mg IM injection	PK Sampling schedule for each injection	Endpoint
As per protocol	Pass required	1 st Dose – Day 0 2 nd Dose – Day 28 3 rd Dose – Day 56 4 th Dose – Day 84 5 th Dose – Day 112 6 th Dose – Day 140	Day 0 (predose, +1, 2, 4, 8, 12 & 24 hours), 1.5, 1.75, 2, 3, 5, 7, 10, 14, 17, 21, 24, 28 Day 56 Day 84 Day 112 Day 140 Day 140 (1, 2, 4, 8 & 12 hours), 141, 141.5, 141.75, 142, 143, 145, 147, 150, 154, 157, 161, 164, 168, 182, and 196	Day 28 and Day 168 trough level measurement

## 2 INTRODUCTION: BACKGROUND INFORMATION AND SCIENTIFIC

### 2.1 BACKGROUND INFORMATION

NTX is a synthetic derivative of thebaine, a minor constituent of opium. It is a nonspecific pure opioid antagonist. NTX binds competitively to all classes of opioid receptors with the following order of preference  $\mu > \kappa > \delta$ , with a high affinity for the  $\mu$ -opioid receptor. It blocks the effects of opioids by competitive binding at opioid receptors. NTX is approved by the FDA for the treatment of opioid dependence/opioid use disorder (OUD) and is also approved for the treatment of alcohol use disorder. NTX is currently registered in USA as a once daily oral formulation containing 50 mg of NTX and as a once-monthly injectable formulation containing 380 mg of NTX (Vivitrol).

#### 2.1.1 *Metabolism of Naltrexone*

NTX is well absorbed orally (96%), but it undergoes a significant first pass metabolism resulting in only 5 to 40% oral bioavailability. NTX is extensively metabolized in humans. Production of the primary metabolite, 6 $\beta$ -naltrexol (6 $\beta$ N), is mediated by dihydrodiol dehydrogenase, a cytosolic family of enzymes. Two other minor metabolites are 2-hydroxy-3-methoxy-6 $\beta$ -naltrexol and 2-hydroxy-3-methoxy-naltrexone. NTX and 6-BN terminal half-life values have been reported as ranging from 2 to 10 hours for NTX and 7.5 to 13 hours for 6-BN. Both NTX and 6-BN are excreted primarily by the kidneys. There is a large amount of variation in the metabolism and PK of NTX. In one study, the enzyme kinetics of the formation of 6-BN from NTX using human liver cytosol preparation showed a 2.9 fold variability in Vmax, a 3.2 fold variability in Km and a 7.7 fold variability in intrinsic clearance. The systemic clearance of NTX supersedes the hepatic blood flow, suggesting the NTX is highly extracted and extra hepatic sites of drug metabolism exist.

#### 2.1.2 *Clinical Use of Naltrexone*

While NTX is a potent antagonist and efficiently blocks the effects of exogenous opioids such as heroin, the success of NTX for the treatment of opioid dependence has been limited by poor patient compliance with the oral formulation. Unlike alternative pharmacotherapies for opioid dependence such as methadone and buprenorphine, NTX has no positive reinforcing effects, ceasing NTX has no withdrawal or negative consequences. Thus, there is little incentive to continue taking the oral formulation, with patients often stopping the medication and returning to opioid use. After opioid detoxification, patients are likely to have reduced tolerance to opioids. As the blockade of exogenous opioids provided by NTX wanes and eventually dissipates completely, patients who have been treated with NTX may respond to lower doses of opioids than previously used, just as they would shortly after completing detoxification. This could result in potentially life-threatening opioid intoxication (respiratory compromise or arrest, circulatory collapse, etc.) if the patient uses previously tolerated doses of opioids.

Better NTX compliance has been observed when a responsible adult is available to supervise daily NTX dosing. It has been reported that the method of daily oral NTX treatment is not an effective long term treatment in most patients. Clinical data has indicated that poor medication compliance occurs with daily oral NTX maintenance treatment for opioid dependence. It has been proposed that the development of a sustained release NTX preparation would combat these issues and lead to improved outcomes for opioid users.

### 2.1.3 *Sustained Release Preparations*

Wise (1984) developed a NTX (70%)-poly(D,L-lactide-co-glycolide) copolymer (30%) implant, which was the first biodegradable drug delivery system approved by the FDA for clinical testing, but was limited by “burst release” in human trials. Previous findings also suggested that polymeric NTX sustained release systems are biocompatible formulations. Additionally, several dosage forms have also been proposed. For example, a NTX-poly(lactic acid) composite, which had an effective blocking action to morphine in rats for 24 days; NTX-copolymer (90% L-lactic acid and 10% glycolic acid) beads, which would provide constant NTX levels for one month, and a NTX pamoate linear poly(ortho esters) disk, which released NTX pamoate for 21 days.

### 2.1.4 *Investigational Product: Vivitrol IM 380 mg*

In 2006, a 30 day NTX intramuscular injection known as Vivitrol (Alkermes) was approved by the FDA for the treatment of alcohol dependence, and it was also approved in 2010 for the treatment of opioid dependence. Vivitrol consists of a NTX PLGA microsphere suspension delivered intramuscularly via an injection. Some studies revealed that a 380 mg injection can produce a mean trough naltrexone blood level above 1.33 ng/ml for approximately four weeks.

Vivitrol PK will be captured in the present study to be used as a reference product in [REDACTED]  
[REDACTED] drug application for the OLANI product which is being developed under [REDACTED]  
[REDACTED]

## 2.2 STUDY RATIONALE

This is a Phase I, single-center, single arm, open-label study to determine PK parameters for Vivitrol 380 mg IM which is an FDA approved formulation. The PK characteristics of Vivitrol can then be used as the approved comparator product in a [REDACTED] application for OLANI.

Participants will be healthy volunteers with no opioid or other substance use disorders and no other significant medical or mental health disorders. It should be noted that participants from Clinical Trial GM 0017 have already received the OLANI treatment and have subsequently provided two consecutive plasma levels of NTX <0.1 ng/mL. Only these participants shall be offered recruitment into the study to allow for the inter-individual comparison of Vivitrol and OLANI PK parameters.

Note: In the future, an expansion of this protocol is planned in order to include additional participants that initially receive 2 doses of Vivitrol followed by the OLANI treatment (i.e. the ‘cross-over’ group). This expansion may occur under this same protocol ID or a new protocol ID.

## 2.3 POTENTIAL RISKS AND BENEFITS

### 2.3.1 *Known Potential Risks*

The following sections (1-11) are taken from *Section 5 of the Vivitrol US Prescribing Information* which should be consulted for detailed information.

#### 1. Vulnerability to Opioid Overdose

After opioid detoxification, patients are likely to have reduced tolerance to opioids. VIVITROL blocks the effects of exogenous opioids for approximately 28 days after

administration. However, as the blockade wanes and eventually dissipates completely, patients who have been treated with VIVITROL may respond to lower doses of opioids than previously used, just as they would have shortly after completing detoxification. This could result in potentially life-threatening opioid intoxication (respiratory compromise or arrest, circulatory collapse, etc.) if the patient uses previously tolerated doses of opioids. Cases of opioid overdose with fatal outcomes have been reported in patients who used opioids at the end of a dosing interval, after missing a scheduled dose, or after discontinuing treatment.

Patients should be alerted that they may be more sensitive to opioids, even at lower doses, after VIVITROL treatment is discontinued, especially at the end of a dosing interval (i.e., near the end of the month that VIVITROL was administered), or after a dose of VIVITROL is missed. It is important that patients inform family members and the people closest to the patient of this increased sensitivity to opioids and the risk of overdose.

There is also the possibility that a patient who is treated with VIVITROL could overcome the opioid blockade effect of VIVITROL. Although VIVITROL is a potent antagonist with a prolonged pharmacological effect, the blockade produced by VIVITROL is surmountable. The plasma concentration of exogenous opioids attained immediately following their acute administration may be sufficient to overcome the competitive receptor blockade. This poses a potential risk to individuals who attempt, on their own, to overcome the blockade by administering large amounts of exogenous opioids. Any attempt by a patient to overcome the antagonism by taking opioids is especially dangerous and may lead to life-threatening opioid intoxication or fatal overdose. Patients should be told of the serious consequences of trying to overcome the opioid blockade.

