## 5 STUDY ENROLLMENT AND WITHDRAWAL

### 5.1 PARTICIPANT INCLUSION CRITERIA

Healthy participants without a DSM 5 - Substance Related Disorders classification will be recruited for this study. Participants will be assessed for their general health and mental health status.

Participants will be required to undergo a NCT to confirm opiate naivety before administration of the IP.

To qualify for the study participation, participants have to:

- Have completed GM 0017 (i.e. been administered OLANI (3.6 gram) and provided two consecutive monthly blood samples of NTX below 0.1 ng/mL)
- Men or women aged at least 18 ( $\geq 18$ ) and no older than 57 ( $< 58$ ), without DSM 5 - Substance Related Disorders classification; in sustained remission is not exclusionary
- Able and willing to comply with the requirements of the protocol
- Able and willing to provide written informed consent
- Willing to undergo an injection of NTX to allow for investigational drug administration in the intramuscular tissue
- Have an initial weight between 45.3 and 81.6 kilograms (inclusive) or have a BMI inclusive of 18.5 to 30.0.

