#### 5.4.2.1 Participant Monitoring and Removal from Study

The psychiatrist and/or therapist will assess appropriateness for continuation in the research study on a continuous basis and will remove from the trial participants with significant clinical deterioration or noncompliance of a type which could be dangerous. Criteria for removal from the study will include:

1. Clinical deterioration which cannot be managed safely in the context of outpatient treatment. This would include a participant who becomes suicidal, or a participant who goes on drug binges (including non-opiate drugs).
2. Elevation of liver enzymes  $>3$  times normal. The PI or a study physician is available 24 hours/day by phone in case of emergency.

For those who withdraw from the study may request to withdraw from data collection and have no further contact with study site. Participants shall be informed that for a period of time 30 days after their last Vivitrol injection there may a risk that opioid based medication may have a reduced affect. There is no option to remove Vivitrol from a participant.

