#### ***7.3.6 Early Termination Visit***

Any participants that are withdrawn will be requested to attend Clinilabs for an early termination /withdrawal visit as outlined in Table 7-1. Participants will be advised of their option as outlined in section 5.4.2.

A follow-up visit may be conducted 30 days after the last scheduled on-study visit and is required only if a participant has ongoing AEs or laboratory abnormalities at the last on-study visit. An in-clinic follow-up visit must be conducted 30 days after the last scheduled on-study visit for an AE requiring laboratory testing for participants with the following conditions at the last on-study visit: ongoing AEs, SAEs regardless of attributability, any laboratory abnormalities considered to be AEs or potentially harmful to the participant. For in-clinic follow-up visits, assessments performed should reflect what is considered medically necessary to assess the event(s).

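### The opioid message for withdrawing participants in section 5.4.2.1 omits the increased-sensitivity and overcoming-blockade warnings in the protocol's own section 2.3.1, item 1

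*Combined protocol and SAP*

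**What the plan says.** Section 5.4.2.1 (Participant Monitoring and Removal from Study) sets out what those who leave are to be informed of: "for a period of time 30 days after their last Vivitrol injection there may a risk that opioid based medication may have a reduced affect". It adds that the injection cannot be removed and that those who withdraw may ask for no further contact with the site. It makes no other statement about opioids.

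Section 7.3.6 (Early Termination Visit) adds no opioid message of its own: "Participants will be advised of their option as outlined in section 5.4.2".

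Section 2.3.1, item 1 (Vulnerability to Opioid Overdose), taken from the US prescribing information, describes blockade of about 28 days that then wanes, after which "patients who have been treated with VIVITROL may respond to lower doses of opioids than previously used". It continues: "Cases of opioid overdose with fatal outcomes have been reported in patients who used opioids at the end of a dosing interval", and it names missed doses and discontinuation as further settings for those deaths. On what patients should hear, it says: "Patients should be alerted that they may be more sensitive to opioids, even at lower doses, after VIVITROL treatment is discontinued". It also says they should be told the serious consequences of trying to overcome the blockade, and that they should make their families aware of the increased sensitivity.

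**The concern.** The protocol gives staff a specific message to deliver when a participant withdraws, and that message covers one of the opioid risks described in the risk section. The part left out is the part that section 2.3.1 links to fatal overdose.

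Three features of the plan make the exit message matter. A past substance-related disorder does not bar entry, since section 5.1 says that "in sustained remission is not exclusionary". Section 5.4.2.1 itself lists drug binges as grounds for removal. Because leavers may decline all further contact, the message at exit could be the last safety information they receive from the study. What is at stake is participant safety, not the pharmacokinetic estimates.

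**Working it through.** No sample size, power or event figure is involved, so the check is a comparison of texts.

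**Step 1. Content of the two passages.**

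| Element | Section 2.3.1, item 1 | Section 5.4.2.1 |
|---|---|---|
| Opioids may have less effect while blockade lasts | Yes (about 28 days) | Yes (30 days) |
| Blockade wanes and lower doses may then act | Yes | Not stated |
| Patients should be alerted to greater sensitivity after stopping | Yes | Not stated |
| Patients should be told of the danger of trying to overcome blockade | Yes | Not stated |
| Overdose named as an outcome | Yes, including deaths | Not stated |

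**Step 2. Does another operational section supply the missing content?**

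- 7.3.6 (early termination) refers to 5.4.2 and adds nothing on opioids.
- 7.3.5 (final visit) and 7.3.7 (unscheduled or late visits) contain no opioid message.
- 7.7 (rescue medication) deals with pain relief during the study, not with information at exit.
- 2.1.2 describes overdose after blockade wanes, but as background and not as something to tell participants.
- 7.1.1.1 and 13.3.2 promise an explanation of risks at entry in general terms. The consent form was not available, so its content is unknown.

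**Step 3. Is the warning relevant here?** The change summary for version 0.3 records that the label warnings were added to 2.3.1 at the FDA's request. The plan also foresees some opioid exposure: 7.5 permits opioids with approval, 7.7 names opioid-type analgesics, and 10.4.3 summarises opioid use during the study. Against this, participants are healthy, have no current substance-related disorder, have a negative urine screen for illicit substances and must pass a naloxone challenge.

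**Result.** In the documents available, the stated exit message lacks the sensitivity warning and the warning about overcoming blockade, and no other withdrawal or early-termination text carries them.

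**The case against.** The strongest reply is that the warning is already in the protocol and may well be in the consent form. Section 5.4.2.1 says what must be conveyed; it does not say that nothing else may be. That stands. It means no one can conclude from these documents that participants are told only about reduced effect, or that they are never warned. It does not remove the gap in the stated text, because general disclosure at entry does not complete a specific instruction for exit.

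A second reply is that the label text mainly describes people who have been through opioid detoxification, and these are healthy volunteers. This also stands and keeps the absolute risk low. It does not make the warning irrelevant, given who may be enrolled and why they may be removed. The remission clause is, however, not specific to opioids.

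A third reply is that the cross-reference in 7.3.6 concerns the participant's option, which may mean only the choice to stop data collection and contact. That reading is fair, and it leaves the early-termination section with no opioid message by any route.

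A reader might also infer three stronger points that the documents do not support:

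- **The two sections contradict each other.** They do not. Residual blockade followed by heightened sensitivity is a coherent sequence; the withdrawal text is incomplete.
- **28 against 30 days is an error.** Section 2.3.1 says "VIVITROL blocks the effects of exogenous opioids for approximately 28 days", and a two-day difference falls within that approximation. Section 2.1.4 also describes the product as a 30-day injection.
- **About 3 of 15 participants (15 − 12 = 3, or 20%) would leave under this message.** Section 5.3.1 defines completion as at least 75% valid PK samples, including the Day 28 and Day 168 troughs. The three are expected to fall short of that standard; they are not a count of withdrawals.

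**Conclusion.** The point holds as one of incomplete content: the exit message in 5.4.2.1 omits two warnings that 2.3.1, item 1 says patients should receive. Its size cannot be put as a number, because the documents give no withdrawal rate. Absolute risk in this population is low and the pharmacokinetic results are untouched. The point is still worth acting on because the omitted content concerns a potentially fatal outcome and the correction is small.

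The conclusion rests on the protocol text alone. If the participant information already carries both warnings, what remains is an inconsistency inside the protocol. The documents do not show whether it does.

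**What to change.** The sponsor should reconcile section 5.4.2.1 with section 2.3.1, item 1, so that the stated exit message and the risk section agree. It should then check the early-termination text in 7.3.6 and the participant information for consistency with the result. The clinical wording is the sponsor's to decide, and none is proposed here.

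The cost is a sentence or two in the next amendment and, if needed, in the participant information. No visit, procedure or analysis changes.
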